Intent-to-treat analyses were employed. Missing data were addressed through Multiple Imputation in Mplus (Enders, 2010). The majority of variables were completed for more than 90% of cases. Descriptive analyses were conducted to assess the implementation outcomes of fidelity, clinical utility, provider and caregiver perceptions of understanding the caregivers' values, and satisfaction with the intake. Additionally, linear regressions tested condition effects on caregiver and provider satisfaction, and the extent to which the provider understood the caregivers' values or what is important to them. Next, logistic and linear regressions examined condition effects on subsequent treatment engagement and response. Exploratory moderation analyses examined the main and interactive effects of language of service delivery (English versus Spanish) with study condition (CA versus CFI+CA) on dependent variables. To interpret effects, adjusted odds ratios and probabilities were calculated for logistic regressions and Cohen's d effect sizes were calculated for linear regressions. An alpha threshold of .25 determined inclusion of covariates. Due to condition differences all analyses controlled for length of intake assessment (in minutes), site, caregiver race/ethnicity, daily stress, and language of assessment delivery. Length of intake assessment is also controlled for to account for differences in effects solely related to differences in the amount of time the provider spent with the caregiver. Baseline ECBI score was included as a covariate for the treatment response analyses.

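### Every model adjusts for intake length, which contains the assigned interview, so no planned analysis estimates the effect of adding the CFI; report a model without length for every outcome

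*Combined protocol and SAP*

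**What the plan says.** All of the analysis wording is in the Data Analysis section of the combined protocol and SAP.

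- Framework: "Intent-to-treat analyses were employed. Missing data were addressed through Multiple Imputation in Mplus".
- Models for the later outcomes: "Next, logistic and linear regressions examined condition effects on subsequent treatment engagement and response". Linear regressions are also used for satisfaction and for provider understanding.
- Covariates: "Due to condition differences all analyses controlled for length of intake assessment (in minutes), site, caregiver race/ethnicity, daily stress, and language of assessment delivery". For one outcome there is an addition: "Baseline ECBI score was included as a covariate for the treatment response analyses".
- Covariate selection: "An alpha threshold of .25 determined inclusion of covariates".
- A second reason is given for length: "Length of intake assessment is also controlled for to account for differences in effects solely related to differences in the amount of time" (the sentence goes on to say time the provider spent with the caregiver).
- Binary results are read as follows: "To interpret effects, adjusted odds ratios and probabilities were calculated for logistic regressions".

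Other sections define the pieces. Procedures places randomization after consent and before the intake interview. The CFI+CA section describes that arm as the CA with the CFI added. Intake Assessment Length defines the recorded minutes as covering consent and whichever interview was assigned. Objectives frames the trial as testing the incremental utility of augmenting the CA with the CFI.

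**The concern.** A baseline covariate cannot be changed by assignment, so adjusting for it leaves the randomized comparison intact. Intake length is different: one arm receives an extra 16-item interview inside the period being timed. Holding length fixed removes whatever the CFI does through a longer intake. It also compares CFI families with CA families whose intakes ran equally long, perhaps for other reasons such as case complexity or caregiver engagement. Randomization does not balance those reasons once length is held fixed.

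At stake is what the reported condition effects mean. A service deciding whether to add the CFI would want the effect of adding it, extra time included. As described, no model gives that.

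**Working it through.** **1. Is length affected by assignment?** The sequence across sections is consent, randomization, intake interview by arm, then one total time in minutes that includes that interview. CFI+CA contains everything in CA plus the CFI. Consent time precedes randomization, but only the total is described as recorded. Data Analysis itself lists length among the variables that differed by condition. So length is, at least in part, a post-randomization consequence of arm.

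**2. Is there any model without it?** None is described. The covariate sentence covers all analyses, and no exception is made for the exploratory language models.

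**3. How far apart could the net and total effects be?** The plan gives no figure on this, so the inputs below are assumptions, apart from the OR of 2.5 taken from the power statement in Procedures. Let s be the arm difference in length in within-arm SDs and b the log OR per SD of length. Approximately, total log OR = ln(2.5) + b × s, with ln(2.5) = 0.916.

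| s | b = +0.3, formula | simulated | b = −0.3, formula | simulated |
|---|---|---|---|---|
| 0.5 | exp(1.066) = 2.90 | 2.90 | exp(0.766) = 2.15 | 2.14 |
| 1 | exp(1.216) = 3.37 | 3.30 | exp(0.616) = 1.85 | 1.87 |
| 1.5 | exp(1.366) = 3.92 | 3.87 | exp(0.466) = 1.59 | 1.57 |

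The simulated values come from 2,000 stacked replicates of n = 89 at a 50% event rate. As an extreme case, an effect of OR 2.5 was made to run wholly through time (shifts of 1 or 2 SD, event rates 20%, 35% and 50%). The length-adjusted log OR was then −0.04 to 0.03, while models without length gave 0.78 to 1.03.

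**4. What does adjustment do to precision?** If length is unrelated to outcome, the variance of the condition effect is multiplied by f = 1 + p(1−p)s², with p = 44/89 (1:1 allocation assumed). In a linear model, if length has within-arm correlation r with the outcome, the factor becomes about (1−r²)f. Break-even is at r = √(1−1/f).

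| s | f | 89/f | break-even r |
|---|---|---|---|
| 0.25 | 1.02 | 88 | 0.12 |
| 0.5 | 1.06 | 84 | 0.24 |
| 1 | 1.25 | 71 | 0.45 |
| 1.5 | 1.56 | 57 | 0.60 |

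At s = 0.5 the linear factor is 1.06 at r = 0, 1.06 × 0.91 = 0.97 at r = 0.3, and 1.06 × 0.75 = 0.80 at r = 0.5. Simulation gave 1.08, 0.97 to 0.99 and 0.82 to 0.84. The interval can therefore widen or narrow.

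**5. Model size for the binary outcomes** (first-session attendance, first-module completion, response). Slopes: condition 1, length 1, site 2 (three sites), race/ethnicity at least 1, stress 1, language 1, making at least 7. Response adds baseline ECBI, making at least 8. With 89 families, events per slope are at most 44/7 = 6.3, or 44/8 = 5.5 for response.

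Simulation at OR 2.5 (4,000 replicates; assumed event rates 30%, 50% and 85%; assumed covariate mix, length shift 1 SD):

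- Maximum likelihood (ML) median OR was 2.63 to 2.80 with 7 slopes and 2.72 to 2.89 with 8, a shift of 0.09 to 0.18 SD. Coverage of 95% intervals was 94.3% to 96.0%.
- Firth median OR was 2.39 to 2.51.
- With 8 slopes at a 50% rate, RMSE was 0.628 for ML and 0.540 for Firth. Power was 0.434 for ML Wald and 0.412 for Firth profile.
- ML type I error at OR 1 (1,500 replicates, 7 slopes without length) was 0.054, 0.063 and 0.045 at the three rates, with Monte Carlo error 0.006.

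**The case against.** The best defence is that the adjustment is deliberate and disclosed. The authors wanted to know whether the CFI does more than buy extra minutes with the provider. That is a legitimate question, and it is the reason to keep the model. It does not make this the effect of assignment. The estimate also has a causal meaning only if length and outcome share no unmeasured causes, an assumption the plan does not state.

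It is also fair to say that incremental utility does not literally mean total effect, and that families can be analysed in their assigned arms whatever covariates are used. Both stand. The total effect is still the natural reading of the objective and of the intent-to-treat label, and it is missing.

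Four stronger readings are tempting but unsupported:

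- That length adjustment hides a benefit. The direction is unknown; the total effect could be larger or smaller than the net one.
- That it widens every interval. In the linear models it can narrow them, as step 4 shows.
- That it takes the effective sample below the plan's 82. That figure is a recruitment minimum, not an effective size after adjustment. It could not be reproduced either: a two-sided, two-arm comparison at OR 2.5 with 80% power needs at least 154 in total.
- That the logistic models are invalid for want of a small-sample correction. The ML shift is small, and type I error and coverage are near nominal. Non-convergence was at most 0.1% at 30% and 50% rates and 5% to 9% at 85%. With 8 slopes it reached 12%, 2% and 19% at the three rates only when the 89/11 race/ethnicity split given for children was assumed for caregivers.

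**Conclusion.** The point holds as a mismatch between the stated objective and every model described. That length contains the assigned interview, is adjusted for throughout and is never left out follows from the text alone and needs no assumed figure. The consequence in this trial cannot be sized. Under the assumed inputs, a net OR of 2.5 corresponds to total ORs from 1.57 to 3.87, and the precision effect may go either way. The change should be made, but the existing model remains a usable answer to a different, secondary question. The small-sample issue in the binary models is minor and does not carry the point.

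**What to change.** 1. For every outcome, report a model without intake length as the intent-to-treat estimate of adding the CFI. Keep site, language, caregiver race/ethnicity and daily stress, plus baseline ECBI for response. Show it beside the original model, and label it post hoc, because data collection ended in March 2019.
2. Relabel the length-adjusted model as a secondary analysis of the effect net of provider time. State that it assumes no unmeasured common causes of intake length and outcome, which randomization does not ensure.
3. State whether daily stress and ECBI were completed before the assigned interview. Procedures puts the questionnaires within the intake, Demographics says only that stress was collected at intake, and no timing is given for baseline ECBI. Note too that the remaining covariates were chosen for observed condition differences.
4. Optional sensitivity analysis for the three binary outcomes: Firth logistic regression with profile penalized-likelihood intervals, intercept-corrected probabilities and stated pooling over imputations. It lowers RMSE and keeps estimates finite but adds no power.

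The cost of items 1 to 3 is a re-run on data already held plus changes of wording. Pooling Firth fits over imputations is extra work; Mplus is named only for the imputation. The main downside is interpretive: a benefit in the model without length may come from extra provider time rather than CFI content, which is why the secondary model stays.
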